## 1.2 Purpose

This Phase 2 study aims to determine the most effective and tolerable dose at the shortest dosing regimen of the investigational drug KAF156 and a Solid Dispersion Formulation of lumefantrine (LUM-SDF) in combination in adult/adolescent and pediatric patients with uncomplicated *P. falciparum* malaria. Different dose combinations and dosing regimens (i.e., 3-, 2-, and 1-day regimens) of KAF156 and LUM-SDF in combination and a reference product Coartem® will be assessed.

This study is set up in a three-part sequential design. Following the PK Run-in Part, Part A of the study will determine in adults and adolescents (greater than or equal to 12 years of age and with a body weight  $\geq 35.0$  kg) the most effective and tolerated dose regimens to be carried forward into Part B which will be conducted in pediatric (2 to < 12 years old and with a body weight  $\geq 10.0$  kg) population. Combined data obtained from Parts A and B will then form the basis for identifying the dose regimen(s) that should be further investigated in Phase 3 development in adults and children down to 2 years of age.

Coartem® will be used as a control for trial sensitivity in Parts A and B so as to evaluate if any significant safety issues or low efficacy results observed in the experimental treatment groups for both adults/adolescents and children are due to treatment or population. It will also provide preliminary relative efficacy for experimental treatment groups compared to the control although it's not statistically powered to show non-inferiority or superiority.

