**Table 3-2 Cohort Success Criteria**

Efficacy	The lower limit of 2-sided 95% exact confidence interval for PCR corrected ACPR at Day 29 is greater than 80%
Safety	A comprehensive assessment of AEs, SAEs, lab data and ECG for investigational and reference product (Coartem ® ) by DMC/Novartis will determine the tolerability success criteria for the cohorts

If needed, secondary efficacy parameters can also be evaluated to discriminate between cohorts in Part A.

Selected cohorts that pass the efficacy/safety hurdles will be further evaluated in Part B.

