**Table 6-2 12-Lead ECG assessments (triplicate) for all patients (PK Run-in Part, Part A and Part B)**

Epoch	Screen		Treatment 														Follow-up						UNS		
	1	99	101						102				199				201	202	203	204	205	299			
Visit Numbers 													EOT Epoch / premature discontinuation									End of Follow up / PSW			
Study Day			1						2				3				4	5	8	15	29	43			
Window			±0 day						±0 day				±0 day				±0 day	+1 day	±1 day	±2 day	±4 days	±4 days			
Time (post-dose) in hours	-24 to <0		0	1	3	6	8	12	18	24	27	30	36	48	51	54	60	68	72	96	168	336	672	1008	
KAF-LUM SDF 1D cohort		x			x	x			x 	x		x 									x			x	
KAF-LUM SDF 2D cohort		x				x 				x	x	x		x							x			x	
KAF-LUM SDF 3D cohort		x				x 				x				x	x	x			x		x			x	
Coartem cohort		x				x 											x				x			x	

**Note: ECG's should be taken in triplicate within 5 minutes after resting for at least 10 minutes in the supine position to ensure a stable heart rate according to the ECG investigator manual. Also, ECG's should be taken before any other procedure taken at the same nominal time point is performed. For Scheduled time ≤ 2 h ± 10 min; 2 to < 24 h ± 30 min; ≥ 24 to 72 h ± 2 h; > 72 h ± 24 h.**

UNS = Unscheduled visit

EOT = End of Treatment

[figure not shown]
PSW = Premature Study Withdrawal

X = assessment to be recorded on clinical data base

 Patients will be admitted to the hospital on Day 1 and will remain in the hospital under close supervision until they are discharged by the investigator or designee on Day 4.

 Visit structure given for internal programming purpose only.

 ECG assessment at this time point to be done for patients in Part A only, ECG assessments will be repeated in case of abnormalities.

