### 9.5.2.4 ECGs

Descriptive summary statistics for the baseline, each study visit, and change from baseline to each study visit will be presented for heart rate, PR interval, QRS interval, RR interval, QT interval, QTcB (QT interval corrected for heart rate according to Bazett) and QTcF (QT interval corrected for heart rate according to Fredericia) for each treatment group. Number and percentage of patients with abnormal values (such as QTc > 480 ms and > 500 ms or HR < 50 /min) and changes from baseline (such as increases in QTc for  $\geq 30$  ms and  $\geq 60$  ms) will be tabulated at each time point and at the maximum value by treatment group in the form of a categorical analysis.

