2.8.3 Other safety data

2.8.3.1 ECG and cardiac imaging data

The following quantitative variables will be summarized for averaged triplicate ECG: heart rate, RR interval, PR interval, QRS interval, QT interval, QTcB (QT interval corrected for heart rate according to Bazett) and QTcF (QT interval corrected for heart rate according to Fredericia).

Descriptive summary statistics for the change from baseline for each post-baseline visit will be performed by ECG parameters and treatment group.

Patients with notably high QT, HR and fever ($\geq 37.5^\circ\text{C}$ for *axillary* or $\geq 38.3^\circ\text{C}$ for other routes) will be provided.

To assess the temporal correlations mean change of QTcF over time, mean change of ECG HR over time, mean change of temperature over time, and PK concentration of KAF156 and lumefantrine over time will be plotted with all panels aligned on the x-axis (Time after dosing).

QTc will be summarized categorically by computing the number and percentage of patients at each time point and at the maximum post baseline value with following:

- QT, QTcF, or QTcB
 - > 450 and ≤ 480 ms
 - > 480 and ≤ 500 ms
 - > 500 ms
 - Increase from Baseline of ≥ 30 ms to < 60 ms
 - Increase from Baseline of ≥ 60 ms
- HR for age ≥ 18 years
 - Increase from baseline $>25\%$ and to a value > 100 bpm
 - Decrease from baseline $>25\%$ and to a value < 50 bpm
- HR for age < 18 years
 - $>$ upper limit of normal (ULN) defined in Table 2-3
 - $<$ lower limit of normal (LLN) defined in Table 2-3
- PR

- Increase from baseline >25% and to a value > 200 ms
- New value of > 200 ms
- QRS
 - Increase from baseline >25% and to a value > 120 ms
 - > 120 ms

Table 2-3 Normal heart rates (resting) by age

Age (years)	Normal range bpm
1 - ≤ 3	70 - 110
3 - ≤ 6	65 -110
6 - ≤12	60 -95
>12	55 -85

Source: Nelson Textbook of Pediatrics, 18th Edition

A line plot by patient (Spaghetti plot) will be provided by visit and treatment group.

In addition, shift tables comparing baseline ECG results (normal, abnormal, not available, total) with the post-baseline results will be provided by visit and at the worst post-baseline result (normal, abnormal, not available, total).

A listing of all newly occurring or worsening abnormalities as compared with baseline will be provided, as well as a by-patient listing of all quantitative ECG parameters.

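### Notable QTc is tabulated by arm at each patient's maximum, but the KAF156 regimens have about twice as many scheduled post-baseline ECGs as Coartem, so the maximum and worst-value columns are not like-for-like with the control

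*SAP*

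**What the plan says.** SAP 2.8.3.1 plans the categorical QTc summary as follows: "QTc will be summarized categorically by computing the number and percentage of patients at each time point and at the maximum post baseline value". The categories are QT, QTcF or QTcB in bands above 450, 480 and 500 ms, and increases from baseline of 30 to below 60 ms and of at least 60 ms. Protocol 9.5.2.4 plans the same summary; abnormal values and changes "will be tabulated at each time point and at the maximum value by treatment group". SAP 2.8.3.1 adds a shift table by visit and at the worst post-baseline result. SAP Table 5-7 takes the most extreme value within a window for notable abnormalities.

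Protocol Table 6-2 sets a different ECG schedule for each regimen. Its footnote 3 marks some cells with "ECG assessment at this time point to be done for patients in Part A only", so Part B has fewer.

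On use, Protocol 1.2 says that Coartem "will be used as a control for trial sensitivity in Parts A and B", so that a safety problem can be attributed to treatment or to population. The safety row of Protocol Table 3-2 is "A comprehensive assessment of AEs, SAEs, lab data and ECG for investigational and reference product", made by the DMC and the sponsor. SAP Table 2-8 sends categorical ECG output to the DMC, including at the end of Part A.

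Neither document limits the maximum to common times, allows for the number of ECGs, or warns that the number differs by arm.

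**The concern.** The maximum of several noisy readings rises with the number of readings. If one arm is read seven or eight times and another four, the first will show more patients over a threshold at their maximum even when the drugs behave identically. Here the extra readings are all on the KAF156 side.

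The by-time-point tables in the same SAP sentence do not have this problem, but they give little common ground. Across all arms they share only 6, 168 and 1008 h in Part A and only 168 and 1008 h in Part B. A reader who wants the share of patients ever notable, KAF156 against Coartem, has only the unequal maximum to look at. ECG results for both products enter the Table 3-2 assessment, so that reader may be the group choosing regimens.

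**Working it through.** **Counting the ECGs.** Marked cells in Table 6-2, leaving out the screening ECG, with Part A-only cells starred:

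| Regimen | Post-baseline times (h) | Part A | Part B |
|---|---|---|---|
| KAF156 1-day | 3, 6, 18*, 24, 30*, 168, 1008 | 7 | 5 |
| KAF156 2-day | 6*, 24, 27, 30, 48, 168, 1008 | 7 | 6 |
| KAF156 3-day | 6*, 24, 48, 51, 54, 72, 168, 1008 | 8 | 7 |
| Coartem | 6*, one late (60 or 68), 168, 1008 | 4 | 3 |

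The late Coartem ECG reads as 60 h in Table 6-2 as extracted, but SAP Table 5-6 has an ECG window for 68 h and none for 60 h. The counts are the same either way.

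Ratios to Coartem: Part A 7/4 = 1.75, 7/4 = 1.75, 8/4 = 2.00. Part B 5/3 = 1.67, 6/3 = 2.00, 7/3 = 2.33.

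**Effect with no drug difference.** The documents state no QTc variance, notable rate or ECG-based power, so there is no figure to reproduce and the inputs below are assumptions. Let the change in QTcF be normal with mean 5 ms, standard deviation SD and common within-patient correlation ρ, the same in every arm and at every time. For k readings and threshold c,

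P(max ≥ c) = 1 − E[Φ((t − √ρ·U)/√(1−ρ))^k], with t = (c − 5)/SD and U standard normal.

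Base case SD 15, ρ 0.5, c = 30 ms, so t = 25/15 = 1.67:

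- 8 readings 21.1%, 4 readings 13.9%: ratio 1.53 (Part A, 3-day against Coartem).
- 7 readings 19.6%, 4 readings 13.9%: ratio 1.42 (Part A, 1-day or 2-day against Coartem).
- 7 readings 19.6%, 3 readings 11.4%: ratio 1.73 (Part B, 3-day against Coartem).

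Over SD 10 to 20 ms and ρ 0.3 to 0.7, the ratio is 1.32 to 1.87 for 8 against 4 and 1.44 to 2.17 for 7 against 3.

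Base case for c = 60 ms, t = 55/15 = 3.67: 0.09% with 8 readings and 0.05% with 4. In arms of 50 and 25 that is well under one patient in each. At SD 20 it is 1.9% against 1.1%.

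**Second model.** Assume instead a probability p of a notable result per ECG, from 1% to 10%, with correlation 0 to 0.8. At p = 1% and no correlation, 1 − 0.99^4 = 3.9% and 1 − 0.99^8 = 7.7%, ratio 1.96. At p = 10% and correlation 0.8, four readings give 19.3% and eight give 24.5%, ratio 1.27. Over the whole range, and including the 7-reading arms, the ratio is 1.22 to 1.96 in Part A and 1.22 to 2.29 in Part B. It is always above 1.

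**Equal numbers of readings.** With three matched readings in each arm (Part A: 6, 168, 1008 h), the second model at p = 2% and correlation 0.5 gives 5.1% in every arm. With two (Part B: 168, 1008 h) it gives 3.7%. The artefact disappears.

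**Windows.** The ECG window for 54 h in SAP Table 5-6 runs from above 52 to 61 h. If the late Coartem ECG is at 60 h, it falls mostly in the window that the 3-day arms also fill, and 3-day against Coartem gains a matched late on-treatment reading (4 against 4 in Part A, 3 against 3 in Part B). If it is at 68 h, its window (above 61 to 70 h) holds no nominal KAF156 ECG.

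**The case against.** The strongest reply is that these are descriptive tables. Table 3-2 sets no QTc cut-off and no test against Coartem, and Protocol 1.2 says the trial is not powered for that comparison. Choosing among KAF156 regimens in Part A sets 7, 7 and 8 readings against one another, where the base case gives 19.6% against 21.1%. SAP 2.8.3.1 also plans change from baseline by visit, mean QTcF over time aligned with heart rate, temperature and drug concentration, patient-level line plots and full listings. All of that stands.

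On size, the ≥30 ms excess of about 7 points is below one standard error of a difference between 50 and 25 patients: √(0.211·0.789/50 + 0.139·0.861/25) ≈ 0.09. That makes it hard to see in one comparison. It does not remove a bias with a fixed direction.

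The model also treats all times alike. The extra KAF156 readings cluster (24, 27, 30 h; 48, 51, 54 h). Letting the non-shared half of the correlation decay over an assumed 6 to 24 h lowers the 3-day ratio from 1.53 to about 1.45 to 1.31. Different ECG timing could also add to or offset the count effect; the 1-day arms, for example, have no ECG between 30 and 168 h, while Coartem has one. These are fair limits on size. They leave the unequal counts, and the silence about them, in place.

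**Conclusion.** The point holds for the maximum and worst-value columns only. The counts are fixed by Table 6-2. The direction follows from them if QTc risk is the same at every time. The size is assumption-based: a ratio of about 1.3 to 1.9 for 8 against 4 ECGs and 1.4 to 2.2 for 7 against 3 for an increase of at least 30 ms, and a negligible base-case excess for at least 60 ms. The absolute-value bands (above 450, 480 and 500 ms) were not modelled, since the documents give no QTc level or spread.

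A reader might infer that the whole QTc comparison with Coartem is biased against KAF156. It is not, because the by-time-point tables and plots are unaffected. A reader might also infer that regimens will be wrongly dropped before Part B or Phase 3. The documents do not show that: the Table 3-2 safety assessment is a judgement over several kinds of data with no QTc rule, so such an effect is possible but unproven. It is a SAP clarification worth making, with no type I error at stake.

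**What to change.** In SAP 2.8.3.1:

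- Keep the all-ECG maximum and worst-value tables for signal detection within each arm. Show scheduled and recorded ECGs per patient by arm, and footnote that these columns are not like-for-like with Coartem.
- For comparison with Coartem, add the notable rate per recorded ECG. This removes the count effect but not the timing effect: in Part A, 6 of the 8 ECGs in the 3-day arms fall within 72 h, against 2 of 4 for Coartem. The footnote should say so.
- Add a supplementary maximum over an equal number of matched SAP analysis windows, including a late on-treatment window where one matches (for example the 54 h window for the 3-day arms if the Coartem ECG is at 60 h).
- Before that, reconcile the 60 h column of Table 6-2 with the 68 h row of SAP Table 5-6.

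The cost is SAP wording and one extra table, with no change to data collection. The drawback is that the matched maximum uses few on-treatment ECGs. Without a matching late window it has only the 6 h reading in Part A and none in Part B, so it could miss a true effect. It must not replace the all-ECG maximum as the safety screen, nor serve as the main between-arm comparison.

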## 15 Appendix 3: Cardiac Alert Threshold Values and Actions

**Table 15-1 Cardiac alert threshold values and actions**

	Values	Actions
QTcF (QTcB for children ≤ 6 years) Cardiac rhythm	QTcB > 500 ms (< 6 years); QTcF > 500 (≥ 6 years). Sustained ventricular tachycardia lasting 30 sec or more, or ventricular fibrillation, or any hemodynamically compromising cardiac arrhythmia	If confirmed by two repeat ECG, check and correct the patient's serum potassium and magnesium immediately. Report as SAE to Sponsor and transmit to eRT immediately for prompt review. Discontinue patient from study therapy. Monitor ECG hourly until at least 2 consecutive hourly ECGs performed are back to baseline
QTcF (QTcB for children ≤ 6 years)  Resting heart rate	Increase from baseline ≥ 60 ms  HR < 50/min with > 25% decrease from pretreatment baseline verified by ECG	If confirmed by two repeat ECG, check and correct the patient's serum potassium and magnesium immediately. Report to Sponsor as AE (unless it meets the SAE criteria as described in Section 7.2.1 ) and transmit to eRT immediately for prompt review.

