2.8.1.1 Adverse events of special interest / grouping of AEs

The adverse events of special interest are defined in the Case retrieval Sheet (CRS) which is updated for each MEDDRA dictionary. The CRS data are stored in RDCRS SAS dataset corresponding to a subset of eCRS SAS view for which the following filtering criteria are applied

-Drug code = KAF156

-the latest version of MedDRA at the time of final database lock.

-End date is null (this means this is the latest CRS version). Potential risks based on the current CRS are listed in [Table 2-1](#).

The number and percent of patients with these special AEs will be summarized. In addition, listings of related adverse events will be provided.

Newly occurring liver enzyme abnormalities and QTcF abnormalities will be summarized (see [Sections 2.8.2 and 2.8.3.1](#))

Table 2-1 List of safety topics of interest

Safety Topic Of Interest	SOC	Search Criteria Details	MedDRA Code	MedDRA Term	MedDRA Level	MedDRA Qualifier
Gastrointestinal tolerability	Gastrointestinal disorders		20000140	Gastrointestinal nonspecific symptoms and therapeutic procedures (SMQ)	MQ2	BROAD
Bradycardia	Cardiac disorders		90003924	Bradycardia [KAF156] (CMQ)	NMQ1	
Gastrointestinal bleeding and ulceration	Gastrointestinal disorders		90003929	Gastrointestinal bleeding and ulceration [KAF156] (CMQ)	NMQ1	
Renal tubular necrosis	Renal and urinary disorders		90003925	Renal tubular necrosis [KAF156] (CMQ)	NMQ1	
Thyroid hypertrophy and hyperplasia	Endocrine disorders		90003926	Thyroid hypertrophy and hyperplasia [KAF156] (CMQ)	NMQ1	
Hepatotoxicity (GenMed)	Hepatobiliary disorders	ALT/AST > 3 ULN; ALP > 2 ULN; TBL>1.5 ULN; ALP >3 ULN and TBL>2 ULN; ALT/ AST > 3 ULN and TBL>2 ULN; ALT/AST > 3 ULN and TBL >= 2 ULN and ALP <2 ULN'	20000006	Drug related hepatic disorders – comprehensive search (SMQ)	MQ2	BROAD
QTc prolongation	Cardiac disorders	Number of pts with notable QTcF, those with QTcF>500 msec, or increase by >=60 msec over baseline. Sustained ventricular tachycardia lasting 30 sec or more, or ventricular fibrillation	20000001	Torsade de pointes/QT prolongation (SMQ)	MQ1	BROAD

Hematological disorders	Blood and lymphatic system disorders		20000027	Haematopoietic cytopenias (SMQ)	MQ1	BROAD
Antimalarial drug resistance	Infections and infestations		90003928	Anti-malarial drug resistance [KAF156] (CMQ)	NMQ1	
Drug – Drug Interactions	General disorders and administration site conditions		90000024	Interactions (PSUR) [STANDARD] (NMQ)	NMQ1	

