Day 15	15	Day 12 - 24	Day 2 - 29	NA
Day 29	29	Day 25 - 33	NA	NA
Day 43/End of study	43	Day 34 and above	Day 30 and above	Day 2 and above

Table 5-6 Analysis visit windows based on study day and time

Analysis Visit	Analysis timepoint	Analysis window for assessment group			
		Temperature	Parasite count	ECG	Rich and Sparse PK
Baseline	0 hrs	up to 0 hrs	up to 0 hrs	up to 0 hrs	up to 0 hrs
Day 1	1 hrs	NA	NA	NA	> 0 - 2 hrs
	3 hrs	NA	NA	>0 - 4 hrs	> 2 - 4 hrs
	6 hrs	>0 - 9 hrs	>0 - 9 hrs	>4 - 12 hrs	>4 - 9 hrs
	8 hrs	NA	NA	NA	NA
	12 hrs	>9 - 15 hrs	>9 - 18 hrs	NA	>9 - 15 hrs
	18 hrs	>15 - 21 hrs	NA	>12 - 21 hrs	>15 - 21 hrs
Day 2	24 hrs	>21 - 27 hrs	>18 hrs to 30 hrs	>21 - 25 hrs	>21 - 25 hrs
	27 hrs	NA	NA	>25 – 28 hrs	>25 - 28 hrs
	30 hrs	>27 - 33 hrs	NA	>28 - 39 hrs	>28 - 33 hrs
	36 hrs	>33 - 42 hrs	>30 - 42 hrs	NA	>33 - 42 hrs
Day 3	48 hrs	>42 - 60 hrs	>42 - 60 hrs	>39 – 49 hrs	>42 - 49 hrs
	51 hrs	NA	NA	>49 – 52 hrs	>49 - 52 hrs
	54 hrs	NA	NA	>52 – 61 hrs	>52 - 63 hrs
	60 hrs	NA	NA	NA	NA
	68 hrs	NA	NA	>61 – 70 hrs	NA
Day 4	72 hrs	>60 hrs to Day 4	>60 hrs to Day 4	>70 hrs to Day 5	>63hrs to Day 4
Day 5	NA	Day 5 - 6	Day 5 - 6	NA	Day 5 - 6
Day 8	NA	Day 7 – 11	Day 7 – 11	Day 6 -25	Day 7 – 11
Day 15	NA	Day 12 - 24	Day 12 - 24	NA	Day 12 and above
Day 29	NA	Day 25 - 33	Day 25 - 33	NA	NA
Day 43/End of study	NA	Day 34 and above	Day 34 and above	Day 26 and above	NA

Table 5-7 Rules for flagging variables

Timing of measurement	Type of data	Rule
Baseline	All data	The last measurement made prior to administration of the first dose of study treatment – note this may include measurements taken on the day of randomization. If a patient did not receive any dose of study treatment then the randomization date will be used.
Post-baseline efficacy	parasite count and temperature	The measurement closest to the target day/time will be used. In the event two measurements are taken equally apart, the first one will be used.(.)
Post-baseline safety	Summary visit information (e.g. lab, ECG, etc.)	The measurement closest to the target day/time will be used. In the event two measurements are taken equally apart, the first one will be used.
Post-baseline safety	Notable abnormalities (e.g. lab, ECG, VS)	The most extreme measurement in the window will be used. Note this means a patient can have a notably high and notably low measurement within a window

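### The across-visit ECG row for low heart rate is evaluated at each patient's maximum post-baseline value, so that row misses transient falls and no other output gives an HR-specific any-time ECG count by arm

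*SAP*

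**What the plan says.** SAP 2.8.3.1 places one sentence above a list covering QT/QTc, HR, PR and QRS: "QTc will be summarized categorically by computing the number and percentage of patients at each time point and at the maximum post baseline value". The HR entries under it include, from age 18, "Decrease from baseline $>25\%$ and to a value < 50 bpm". Under 18 the low criterion is a value below the "lower limit of normal (LLN) defined in Table 2-3", which runs from 55 to 70 bpm by age.

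Protocol 9.5.2.4 has the same rule. It gives as examples of abnormal values "such as QTc > 480 ms and > 500 ms or HR < 50 /min", and says that abnormal values and changes "will be tabulated at each time point and at the maximum value by treatment group in the form of a categorical analysis". Neither document gives a rule for the lowest post-baseline HR.

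Three related provisions matter:
- SAP Table 5-7, for notable abnormalities within a visit window: "The most extreme measurement in the window will be used". It recognises that a patient may have both a high and a low notable value in one window.
- SAP Table 2-1 lists bradycardia as a safety topic of interest.
- Protocol Table 15-1 makes "HR < 50/min with > 25% decrease from pretreatment baseline verified by ECG" a cardiac alert.

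**The concern.** An across-visit row is normally read as the number of patients who met a criterion at any time after dosing. For criteria that look for high values, taking the maximum gives that number. For a low-HR criterion it gives the number of patients who were low at every recorded post-baseline ECG, which is a different and far rarer event.

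What is at stake is the reading of one row on a named KAF156 risk. A value at or near zero in every arm would look like reassurance, yet it would be close to zero by construction whatever the drug did.

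**Working it through.** The documents state no figure for this point, so there is nothing to reproduce. The check is to apply the rule as written.

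**Inputs from the documents.** Protocol Table 6-2 schedules seven post-dose ECGs for a 1-day KAF156 cohort in Part A: 3, 6, 18, 24, 30, 168 and 1008 hours. Protocol 9.8 plans 50 randomised patients per KAF156/LUM-SDF arm.

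**Step 1: what the rule requires.** The adult low criterion is HR < 50 and HR < 0.75 × baseline, which is HR < T with T = min(50, 0.75 × baseline). Under 18, T is the age-specific lower limit of normal. Therefore:
- at the maximum, a patient counts only if max(HR) < T, that is, if all post-baseline ECGs are below T;
- at the minimum, a patient counts if min(HR) < T, that is, if at least one ECG is below T.

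The row at the maximum also needs the 1008-hour ECG (Day 43) to be low, 42 days after a single dose. Whatever the correlation between ECGs, the expected count in that row cannot exceed the expected count at the time point where low values are rarest.

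**Step 2: a worked adult (assumed values).** Baseline is 80, so T = min(50, 60) = 50. Post-dose values in schedule order are 76, 46, 62, 70, 72, 74 and 78.
- Maximum 78: a fall of 2/80 = 2.5%, not counted.
- Minimum 46: a fall of 34/80 = 42.5%, counted.
- 6-hour time point: 46, counted.

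The across-visit row misses this patient and the 6-hour count keeps the patient.

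**Step 3: expected counts per 50 patients.** Let q be the chance that one ECG meets the full low criterion. Both q and independence between ECGs are assumptions. P(at least one of 7) = 1 − (1 − q)^7, and P(all 7) = q^7.

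| q | One time point (50q) | Sum over 7 time points | Ever low (minimum) | Always low (maximum) |
|---|---|---|---|---|
| 1% | 0.5 | 3.5 | 3.40 | 5 × 10⁻¹³ |
| 2% | 1.0 | 7.0 | 6.59 | 6.4 × 10⁻¹¹ |
| 5% | 2.5 | 17.5 | 15.08 | 3.9 × 10⁻⁸ |
| 10% | 5.0 | 35.0 | 26.09 | 5 × 10⁻⁶ |

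Positive correlation within patients would lower the ever-low column and raise the always-low column, subject to the bound in Step 1.

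**Step 4: can the time-point counts replace the row?** Suppose five time points show one patient each. That fits five patients with one episode each, or one patient with five episodes. The number ever affected is known only to lie between the largest single count and the sum, here 1 to 5.

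The counts are also thin. If 10% of 50 patients (5) each had one episode, equally likely at any of the seven ECGs, a given time point would show 5/7 = 0.71 patients on average. The chance of it showing two or more is P(Binomial(50, 0.10/7) ≥ 2) = 0.16.

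**The case against.** The strongest reply is that the signal is covered elsewhere, and much of this stands.

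- **Time-point counts.** The same sentence requires them, and Table 5-7 protects them by taking the most extreme value in the window. A reader might infer that a transient fall disappears from the ECG table, or that the affected row is the only planned patient count from ECGs. The documents support neither inference.
- **Adverse events.** Under Table 15-1 a low-HR alert confirmed by two repeat ECGs is reported as an AE, and SAP 2.8.1.1 summarises patients with AEs of special interest. This can give a once-per-patient bradycardia count. It depends on confirmation and on investigator reporting in an open-label trial, whereas protocol 6.5.5 has the ECGs read centrally by a blinded cardiologist.
- **Pulse table.** Under 18, SAP Table 2-4 uses the same Table 2-3 limits. In adults its rule is ≤ 50 bpm with a fall of at least 15 bpm, which overlaps heavily: a fall of more than 25% to 45–49 bpm always exceeds 15 bpm. The rules still differ at the edges. A change from 55 to 41 (14 bpm, 25.5%) meets only the ECG rule, and one from 65 to 50 (15 bpm, 23.1%) meets only the pulse rule. Pulse is also a separate measurement from the ECG.
- **Shift table and listings.** The shift table uses the worst post-baseline result, but only as normal or abnormal, and listings are not counts by arm.
- **Wording.** The SAP sentence has QTc as its subject, so the maximum may simply have been carried over to the other parameters. That may explain how it arose, but protocol 9.5.2.4 names low HR in the very sentence that orders tabulation at the maximum.
- **DMC.** A reader might infer that the DMC sees the same row, because SAP Table 2-8 lists a categorical ECG output and the DMC plan is to be based on this SAP. That plan is a separate document and is not available, so this cannot be confirmed. The DMC also receives all AEs and notable vital signs.

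**Conclusion.** Wrong as written, limited to one summary row. Read literally, both documents evaluate low HR across visits at the highest post-baseline value, so the row is near zero by construction for any transient effect. The logic in Step 1 needs no assumed incidence. The counts per 50 patients do: they rest on assumed values of q and on independence, and are illustrations, not forecasts.

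The loss is of one specific quantity, the HR-specific number of patients by arm who ever met the low criterion on ECG. Other outputs partly cover the signal but do not supply that number. This does not show that bradycardia would go undetected or that the choice of regimens for Part B would be misled.

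**What to change.** In SAP 2.8.3.1, keep the maximum post-baseline value for QT/QTc, PR, QRS and the high-HR criteria. Evaluate the existing low-HR criteria, with their limits unchanged, at the minimum post-baseline value, so that a patient counts if the criterion is met at least once after the first dose. Keep the counts at each time point.

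Protocol 9.5.2.4 carries the same wording, so align it or record the difference in SAP section 4, which now reports no changes to protocol-specified analyses. Check that the DMC's categorical ECG output uses the same rule.

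The cost is one phrase and one derived minimum per patient from ECG data already collected.
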